**Table 3. Systemic Event Grading Scale**

	Mild (Grade 1)	Moderate (Grade 2)	Severe (Grade 3)	Potentially Life-Threatening (Grade 4)
Vomiting	1-2 times in 24 hours	>2 times in 24 hours	Requires IV hydration	Emergency room visit or hospitalization for hypotensive shock
Diarrhea	2 to 3 loose stools in 24 hours	4 to 5 loose stools in 24 hours	6 or more loose stools in 24 hours	Emergency room visit or hospitalization for severe diarrhea
Headache	Does not interfere with activity	Some interference with activity	Prevents daily routine activity	Emergency room visit or hospitalization for severe headache

**Table 3. Systemic Event Grading Scale**

	Mild (Grade 1)	Moderate (Grade 2)	Severe (Grade 3)	Potentially Life-Threatening (Grade 4)
Fatigue/tiredness	Does not interfere with activity	Some interference with activity	Prevents daily routine activity	Emergency room visit or hospitalization for severe fatigue
Chills	Does not interfere with activity	Some interference with activity	Prevents daily routine activity	Emergency room visit or hospitalization for severe chills
New or worsened muscle pain	Does not interfere with activity	Some interference with activity	Prevents daily routine activity	Emergency room visit or hospitalization for severe new or worsened muscle pain
New or worsened joint pain	Does not interfere with activity	Some interference with activity	Prevents daily routine activity	Emergency room visit or hospitalization for severe new or worsened joint pain

Abbreviation: IV = intravenous.

#### 8.3.4.4. Fever

In order to record information on fever, a thermometer will be given to participants with instructions on how to measure oral temperature at home. Temperature will be collected in the reactogenicity e-diary in the evening daily during the reactogenicity e-diary reporting period. It will also be collected at any time during the reactogenicity e-diary data collection periods when fever is suspected. Fever is defined as an oral temperature  $\geq 38.0^{\circ}\text{C}$  ( $\geq 100.4^{\circ}\text{F}$ ). The highest temperature for each day will be recorded in the reactogenicity e-diary. Temperature will be measured and recorded to 1 decimal place. Temperatures recorded in degrees Fahrenheit will be programmatically converted to degrees Celsius and then categorized according to the scale shown in Table 4 during analysis.

If a fever of  $\geq 39.0^{\circ}\text{C}$  ( $\geq 102.1^{\circ}\text{F}$ ) is reported in the reactogenicity e-diary, a telephone contact should occur to ascertain further details and determine whether a site visit is clinically indicated. Only an investigator or medically qualified person is able to confirm a participant's fever as  $>40.0^{\circ}\text{C}$  ( $>104.0^{\circ}\text{F}$ ). If a participant experiences a confirmed fever  $>40.0^{\circ}\text{C}$  ( $>104.0^{\circ}\text{F}$ ), the investigator must immediately notify the sponsor.

**Table 4. Scale for Fever**

$\geq 38.0\text{-}38.4^{\circ}\text{C}$ ( $100.4\text{-}101.1^{\circ}\text{F}$ )
$>38.4\text{-}38.9^{\circ}\text{C}$ ( $101.2\text{-}102.0^{\circ}\text{F}$ )
$>38.9\text{-}40.0^{\circ}\text{C}$ ( $102.1\text{-}104.0^{\circ}\text{F}$ )
$>40.0^{\circ}\text{C}$ ( $>104.0^{\circ}\text{F}$ )

#### **8.3.4.5. Antipyretic Medication**

The use of antipyretic medication to treat symptoms associated with study intervention administration will be recorded in the reactogenicity e-diary daily during the reporting period (Day 1 through Day 7).

#### **8.3.5. Pregnancy Testing**

Pregnancy tests may be urine or serum tests but must have a sensitivity of at least 25 mIU/mL. Pregnancy tests will be performed in WOCBP at Visit 1, before the administration of the dose of study intervention. A negative pregnancy test result will be required prior to the participant's receiving the study intervention. Pregnancy tests may also be repeated if requested by IRBs/ECs or if required by local regulations. In the case of a positive confirmed pregnancy, the participant will not be administered the study intervention and will be withdrawn from the study.

### **8.4. Adverse Events, Serious Adverse Events, and Other Safety Reporting**

The definitions of an AE and an SAE can be found in [Section 10.2](#).

The definitions of device-related safety events (ADEs and SADEs) can be found in [Section 10.8](#). Device deficiencies are covered in [Section 8.4.9](#).

AEs may arise from symptoms or other complaints reported to the investigator by the participant (or, when appropriate, by a caregiver, surrogate, or the participant's legally authorized representative), or they may arise from clinical findings of the investigator or other healthcare providers (clinical signs, test results, etc).

The investigator and any qualified designees are responsible for detecting, documenting, and recording events that meet the definition of an AE or SAE and remain responsible to pursue and obtain adequate information both to determine the outcome and to assess whether the event meets the criteria for classification as an SAE or caused the participant to discontinue the study (see [Section 7.1](#)).

During the active collection period as described in Section 8.4.1, each participant will be questioned about the occurrence of AEs in a nonleading manner.

In addition, the investigator may be requested by Pfizer Safety to obtain specific follow-up information in an expedited fashion.

#### **8.4.1. Time Period and Frequency for Collecting AE and SAE Information**

The time period for actively eliciting and collecting AEs and SAEs (“active collection period”) for each participant begins from the time the participant provides informed consent, which is obtained before the participant’s participation in the study (ie, before undergoing any study-related procedure and/or receiving study intervention), through and including Visit 3. In addition, AEs occurring up to 48 hours after blood draws or collection of

midturbinate swabs must be recorded on the CRF. SAEs will be collected from the time the participant provides informed consent to Visit 4 (approximately 6 months after vaccination).

Deaths, pneumonia, and hospitalizations will be recorded as follows:

- a. If related to ILIs (as defined in Section 8.10.6) or their sequelae: these events will be recorded for the entire study duration on the relevant CRF page related to the ILI visit and will not be reported as SAEs/AEs (see [Section 8.4.7](#)).
- b. If not related to ILIs or their sequelae: these events will be reported as AEs/SAEs as appropriate up to Visit 4.

Follow-up by the investigator continues throughout the active collection period and until the AE or SAE or its sequelae resolve or stabilize at a level acceptable to the investigator.

When a clinically important AE remains ongoing at the end of the active collection period, follow-up by the investigator continues until the AE or SAE or its sequelae resolve or stabilize at a level acceptable to the investigator and Pfizer concurs with that assessment.

For participants who are screen failures, the active collection period ends when screen failure status is determined.

If the participant withdraws from the study and also withdraws consent for the collection of future information, the active collection period ends when consent is withdrawn.

If a participant permanently discontinues or temporarily discontinues study because of an AE or SAE, the AE or SAE must be recorded on the CRF and the SAE reported using the Vaccine SAE Reporting Form.

Investigators are not obligated to actively seek information on AEs or SAEs after the participant has concluded study participation. However, if the investigator learns of any SAE, including a death, at any time after a participant has completed the study, and they consider the event to be reasonably related to the study intervention, the investigator must promptly report the SAE to Pfizer using the Vaccine SAE Reporting Form.

#### **8.4.1.1. Reporting SAEs to Pfizer Safety**

All SAEs occurring in a participant during the active collection period as described in [Section 8.4.1](#) are reported to Pfizer Safety on the Vaccine SAE Reporting Form immediately upon awareness and under no circumstance should this exceed 24 hours, as indicated in [Section 10.2](#). The investigator will submit any updated SAE data to the sponsor within 24 hours of its being available.

#### **8.4.1.2. Recording Nonserious AEs and SAEs on the CRF**

All nonserious AEs and SAEs occurring in a participant during the active collection period, which begins after obtaining informed consent as described in [Section 8.4.1](#), will be recorded on the AE section of the CRF.

The investigator is to record on the CRF all directly observed and all spontaneously reported AEs and SAEs reported by the participant.

As part of ongoing safety reviews conducted by the sponsor, any nonserious AE that is determined by the sponsor to be serious will be reported by the sponsor as an SAE. To assist in the determination of case seriousness, further information may be requested from the investigator to provide clarity and understanding of the event in the context of the clinical study.

#### **8.4.2. Method of Detecting AEs and SAEs**

The method of recording, evaluating, and assessing causality of AEs and SAEs and the procedures for completing and transmitting SAE reports are provided in [Section 10.2](#).

Care will be taken not to introduce bias when detecting AEs and/or SAEs. Open-ended and nonleading verbal questioning of the participant is the preferred method to inquire about AE occurrences.

#### **8.4.3. Follow-Up of AEs and SAEs**

After the initial AE or SAE report, the investigator is required to proactively follow each participant at subsequent visits/contacts. For each event, the investigator must pursue and obtain adequate information until resolution, stabilization, the event is otherwise explained, or the participant is lost to follow-up (as defined in [Section 7.3](#)).

In general, follow-up information will include a description of the event in sufficient detail to allow for a complete medical assessment of the case and independent determination of possible causality. Any information relevant to the event, such as concomitant medications and illnesses, must be provided. In the case of a participant death, a summary of available autopsy findings must be submitted as soon as possible to Pfizer Safety.

Further information on follow-up procedures is provided in [Section 10.2](#).

#### **8.4.4. Regulatory Reporting Requirements for SAEs**

Prompt notification by the investigator to the sponsor of an SAE is essential so that legal obligations and ethical responsibilities toward the safety of participants and the safety of a study intervention under clinical investigation are met.

The sponsor has a legal responsibility to notify both the local regulatory authority and other regulatory agencies about the safety of a study intervention under clinical investigation. The sponsor will comply with country-specific regulatory requirements relating to safety reporting to the regulatory authority, IRBs/ECs, and investigators.

Investigator safety reports must be prepared for SUSARs according to local regulatory requirements and sponsor policy and forwarded to investigators as necessary.

An investigator who receives SUSARs or other specific safety information (eg, summary or listing of SAEs) from the sponsor will review and then file it along with the SRSD(s) for the study and will notify the IRB/EC, if appropriate according to local requirements.

#### **8.4.5. Environmental Exposure, Exposure During Pregnancy or Breastfeeding, and Occupational Exposure**

Environmental exposure occurs when a person not enrolled in the study as a participant receives unplanned direct contact with or exposure to the study intervention. Such exposure may or may not lead to the occurrence of an AE or SAE. Persons at risk for environmental exposure include healthcare providers, family members, and others who may be exposed. An environmental exposure may include EDP, EDB, and occupational exposure.

Any such exposures to the study intervention under study are reportable to Pfizer Safety within 24 hours of investigator awareness.

##### **8.4.5.1. Exposure During Pregnancy**

An EDP occurs if:

- A female participant is found to be pregnant while receiving or after discontinuing study intervention.
- A male participant who is receiving or has discontinued study intervention inseminates a female partner.
- A female nonparticipant is found to be pregnant while being exposed or having been exposed to study intervention because of environmental exposure. Below are examples of environmental EDP:
  - A female family member or healthcare provider reports that she is pregnant after having been exposed to the study intervention by inhalation or skin contact.
  - A male family member or healthcare provider who has been exposed to the study intervention by inhalation or skin contact then inseminates his female partner prior to or around the time of conception.

The investigator must report EDP to Pfizer Safety within 24 hours of the investigator's awareness, irrespective of whether an SAE has occurred. The initial information submitted should include the anticipated date of delivery (see below for information related to termination of pregnancy).

- If EDP occurs in a participant/participant's partner, the investigator must report this information to Pfizer Safety on the Vaccine SAE Reporting Form and an EDP Supplemental Form, regardless of whether an SAE has occurred. Details of the pregnancy will be collected after the start of study intervention and until 28 days after the study intervention.
- If EDP occurs in the setting of environmental exposure, the investigator must report information to Pfizer Safety using the Vaccine SAE Reporting Form and EDP Supplemental Form. Since the exposure information does not pertain to the participant enrolled in the study, the information is not recorded on a CRF; however, a copy of the completed Vaccine SAE Reporting Form is maintained in the investigator site file.

Follow-up is conducted to obtain general information on the pregnancy and its outcome for all EDP reports with an unknown outcome. The investigator will follow the pregnancy until completion (or until pregnancy termination) and notify Pfizer Safety of the outcome as a follow-up to the initial EDP Supplemental Form. In the case of a live birth, the structural integrity of the neonate can be assessed at the time of birth. In the event of a termination, the reason(s) for termination should be specified and, if clinically possible, the structural integrity of the terminated fetus should be assessed by gross visual inspection (unless preprocedure test findings are conclusive for a congenital anomaly and the findings are reported).

Abnormal pregnancy outcomes are considered SAEs. If the outcome of the pregnancy meets the criteria for an SAE (ie, ectopic pregnancy, spontaneous abortion, intrauterine fetal demise, neonatal death, or congenital anomaly), the investigator should follow the procedures for reporting SAEs. Additional information about pregnancy outcomes that are reported to Pfizer Safety as SAEs follows:

- Spontaneous abortion including miscarriage and missed abortion should be reported as an SAE;
- Neonatal deaths that occur within 1 month of birth should be reported, without regard to causality, as SAEs. In addition, infant deaths after 1 month should be reported as SAEs when the investigator assesses the infant death as related or possibly related to exposure to the study intervention.

Additional information regarding the EDP may be requested by the sponsor. Further follow-up of birth outcomes will be handled on a case-by-case basis (eg, follow-up on preterm infants to identify developmental delays). In the case of paternal exposure, the investigator will provide the participant with the Pregnant Partner Release of Information Form to deliver to his partner. The investigator must document in the source documents that

the participant was given the Pregnant Partner Release of Information Form to provide to his partner.

#### **8.4.5.2. Exposure During Breastfeeding**

An EDB occurs if:

- A female participant is found to be breastfeeding while receiving or after discontinuing study intervention.
- A female nonparticipant is found to be breastfeeding while being exposed or having been exposed to study intervention (ie, environmental exposure). An example of environmental EDB is a female family member or healthcare provider who reports that she is breastfeeding after having been exposed to the study intervention by inhalation or skin contact.

The investigator must report EDB to Pfizer Safety within 24 hours of the investigator's awareness, irrespective of whether an SAE has occurred. The information must be reported using the Vaccine SAE Reporting Form. When EDB occurs in the setting of environmental exposure, the exposure information does not pertain to the participant enrolled in the study, so the information is not recorded on a CRF. However, a copy of the completed Vaccine SAE Reporting Form is maintained in the investigator site file.

An EDB report is not created when a Pfizer drug specifically approved for use in breastfeeding women (eg, vitamins) is administered in accordance with authorized use. However, if the infant experiences an SAE associated with such a drug, the SAE is reported together with the EDB.

#### **8.4.5.3. Occupational Exposure**

The investigator must report any instance of occupational exposure to Pfizer Safety within 24 hours of the investigator's awareness using the Vaccine SAE Reporting Form, regardless of whether there is an associated SAE. Since the information about the occupational exposure does not pertain to a participant enrolled in the study, the information is not recorded on a CRF; however, a copy of the completed Vaccine SAE Reporting Form must be maintained in the investigator site file.

#### **8.4.6. Cardiovascular and Death Events**

Deaths will be recorded throughout the study as detailed in [Section 8.4.1](#).

#### **8.4.7. Disease-Related Events and/or Disease-Related Outcomes Not Qualifying as AEs or SAEs**

ILIs and their sequelae, including pneumonia and death, that are potentially consistent with any clinical efficacy endpoint definitions should not be recorded as AEs. These data will be captured as efficacy assessment data only on the relevant pages of the CRF, as these are expected endpoints.

ILIs and their sequelae will not be reported according to the standard process for expedited reporting of SAEs, even though the event may meet the definition of an SAE. These events will be recorded on the ILI visit pages in the participant's CRF within 1 day.

NOTE: However, if either of the following conditions applies, then the event must be recorded and reported as an SAE (instead of a disease-related event):

- The event is, in the investigator's opinion, of greater intensity, frequency, or duration than expected for the individual participant.

OR

- The investigator considers that there is a reasonable possibility that the event was related to study intervention.

ILIs and their sequelae will be reviewed by an internal blinded case reviewer. Any SAE that is determined by the internal case reviewer NOT to meet any clinical primary efficacy endpoint criteria is reported back to the investigator site of incidence. The investigator must report the SAE to Pfizer Safety within 24 hours of being made aware that the SAE did not meet endpoint criteria. The investigator's SAE awareness date is the date on which the investigator site of incidence receives the SAE back from the internal case reviewers.

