## 8.2. Efficacy and/or Immunogenicity Assessments

### 8.2.1. Surveillance for Influenza

Following vaccination, if a participant develops symptoms of per-protocol ILI as detailed in [Section 8.10.6](#), the participant should contact the site and an in-person, home health, or telehealth ILI visit should occur within 5 days of onset of ILI symptoms (see [Section 8.10.6.1](#)). At the ILI visit, assessments should be conducted as specified in [Section 8.10.6.1](#), which will include collection of 2 midturbinate swab samples (1 from each nostril) for testing at a central laboratory using RT-PCR and viral culture testing to detect influenza viruses in the respiratory specimen. **CCI** [REDACTED]

(Cepheid Xpert Xpress CoV-2/Flu/RSV plus test).

Culture testing will only be conducted on swab samples from participants with an RT-PCR-positive swab sample from the corresponding ILI visit.

Midturbinate swabs will be collected by site staff if the ILI visit is conducted in person, or midturbinate swabs will be collected by the participant if the ILI visit is conducted as a telehealth consultation.

Both the central laboratory RT-PCR and viral culture results will be used for the relevant endpoint case definitions as shown in [Table 1](#). Local test results for influenza will also be collected at the ILI visit, if available.

ILIs and their sequelae (including pneumonia and death) that are consistent with the clinical endpoint definition should not be recorded as AEs (see [Section 8.4.7](#) for further details).

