- Discuss contraceptive use as described in [Section 4.2.2](#).
- Record prohibited medication use as described in [Section 6.9.1](#).
- Record any AEs that occur within the 48 hours after the midturbinate swab as described in [Section 8.4](#).
- Record AEs as described in [Section 8.4](#). Note: ILIs and their sequelae that are consistent with the clinical endpoint definition should not be recorded as AEs (see [Section 8.4.7](#) for further details). These data will be captured as efficacy assessment data only on the relevant pages of the CRF, as these are expected endpoints.
- Complete the source documents.

- The investigator or an authorized designee completes the CRFs.

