3.1.1.2. First-Episode LCI Case Derivation With Associated Per-Protocol ILI

For the primary efficacy endpoint, only first-episode LCI cases with per-protocol ILI, with initial symptom onset date between Day 15 (ie, 14 days after vaccination) and the end of the influenza season (all inclusive), or the data cutoff date for performing primary efficacy analysis as determined by the sponsor, will be considered. Additionally, if there are any important protocol deviations before/during ILI onset, the cases from these ILIs will not be included in the evaluable efficacy population analysis.

The important protocol deviations are identified throughout the study via study monitor, medical, and other team member review. In the case in which there are multiple episodes of LCI with per-protocol ILI, only the first-episode that is between Day 15 and the end of the influenza season, or the data cutoff date for performing primary efficacy analysis as determined by the sponsor, will be included as the primary endpoint.

Following the ILI visit being initiated, if new OR recurrent symptoms that meet per-protocol requirements for an ILI visit emerge, there is no minimum time between symptom start and/or resolution that would preclude an additional ILI visit. Investigators should discuss the symptoms with the participant and use their clinical judgment to determine if such new OR recurrent symptoms are part of a single ILI or a second ILI, and therefore if an additional ILI visit is required.

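### Read literally, Protocol 8.4.7 gives a nonserious influenza-negative ILI no way back to the AE page and sends related ILIs to SAE reporting, in conflict with 8.2.1, 8.10.6.1 and Appendix 2

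*Protocol*

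**What the plan says.** Protocol 8.4.7 sets the main rule: "ILIs and their sequelae, including pneumonia and death, that are potentially consistent with any clinical efficacy endpoint definitions should not be recorded as AEs". Such events go only to the efficacy pages of the CRF. A blinded internal reviewer then looks at them, with one return path: "Any SAE that is determined by the internal case reviewer NOT to meet any clinical primary efficacy endpoint criteria is reported back" to the site. A note adds an override. If the investigator thinks the event related to study intervention, or of greater intensity, frequency or duration than expected, "then the event must be recorded and reported as an SAE (instead of a disease-related event").

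Other sections touch the same events:

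- Section 8.2.1 covers ILIs and sequelae "that are consistent with the clinical endpoint definition should not be recorded as AEs". Section 8.10.6.1, on the ILI visit, says the same: "ILIs and their sequelae that are consistent with the clinical endpoint definition should not be recorded as AEs". Both then refer to 8.4.7 for detail.
- Section 8.4.1 covers deaths, pneumonia and hospitalizations related to an ILI as defined by symptoms in 8.10.6. They are recorded "on the relevant CRF page related to the ILI visit and will not be reported as SAEs/AEs".
- Appendix 2, Section 10.2.1, removes from the AE definition the disease under study, unless it is more severe than expected. Section 10.2.3 makes an event serious only when it meets a predefined SAE outcome, and not because it is severe.
- SAP 3.1.1.2 limits primary cases to those "with initial symptom onset date between Day 15 (ie, 14 days after vaccination) and the end of the influenza season" or the data cutoff.

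AEs through 4 weeks and SAEs through 6 months are both primary safety endpoints (Protocol Section 3; SAP 6.1.3.1).

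**The concern.** An ILI is defined by symptoms, whatever the suspected cause (Protocol 8.10.6). Many ILIs will therefore not be influenza, and those are ordinary intercurrent illnesses of the kind an AE table is meant to hold. Section 8.4.7 diverts them on the strength of potential consistency with an endpoint. It asks for entry on the ILI pages within 1 day, when a central laboratory result would not normally be in hand. A later correction step is therefore needed, and the only one described handles serious events.

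The note works in the other direction. Relatedness is not a seriousness criterion, yet a mild ILI judged related is sent to SAE reporting. At stake are the two headline safety proportions, and whether they mean the same thing from one site to the next.

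**Working it through.** The plan gives no figure on this point to reproduce. The check is mainly a comparison of the passages, followed by an illustration on assumed inputs.

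**1. Nonserious ILI, influenza-negative on central testing, onset before Visit 3.**

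- Under 8.4.7 it was potentially consistent with an endpoint when recorded, so it stays off the AE page. It is not an SAE, so the reviewer does not return it.
- Under 8.2.1 and 8.10.6.1 it is not consistent with the endpoint definition once the result is known, so the exclusion does not cover it.
- Under 10.2.1 it is not the disease being studied, so it is an AE, and 8.4.1.2 requires nonserious AEs to be recorded.
- SAP 3.1.2.4 and 6.1.3, in the text that can be read, bring no ILI-page events into the AE table.

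The same event is an AE under three provisions and not under the fourth, to which the first two refer.

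**2. Nonserious ILI judged related.** The note makes it an SAE and offers no nonserious option. Section 10.2.3 makes it serious only if a predefined outcome is met. A worse-than-expected influenza episode shows the same conflict: 10.2.1 readmits it as an AE, while the note files it as an SAE.

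**3. Two tests inside 8.4.7.** The exclusion refers to *any* clinical efficacy endpoint, the return step only to the *primary* one. A serious ILI confirmed only by a local RT-PCR meets a secondary endpoint, so it is excluded at entry, and it fails the primary criteria, so it is sent back as an SAE.

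**4. Direction.** Where 8.4.7 is followed, the 4-week AE proportion is too low. Where the note is applied literally, the SAE proportion is too high.

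**5. Illustration, all inputs assumed.** Let *a* be the share of participants with a nonserious influenza-negative ILI by 4 weeks (1% to 5%), and *b* the share with some other AE (5% to 20%), independent of each other. The full rate is b + a(1 − b) and the recorded rate is b, so the shortfall is a(1 − b).

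- Smallest: 0.01 × 0.80 = 0.8 percentage points, on a full rate of 20.8%; 0.8 / 20.8 = 4% of it.
- Largest: 0.05 × 0.95 = 4.75 percentage points, on a full rate of 9.75%; 4.75 / 9.75 = 49% of it.

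Let *f* be the share of those ILIs judged related and filed as SAEs (1% to 10%). Per 18,100 participants (a column of Protocol Table 7, used only as a denominator), extra SAEs = 18,100 × a × f:

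- 18,100 × 0.01 × 0.01 = 1.8, or 0.01 percentage points.
- 18,100 × 0.05 × 0.10 = 90.5, or 0.5 percentage points.

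ILIs filed as SAEs would also count as AEs, so the shortfall shrinks by the factor (1 − f). Its range becomes 0.8 × 0.90 = 0.72 to 4.75 × 0.99 = 4.70 points. For the given inputs these are ceilings, because they assume every site follows 8.4.7 to the letter.

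**The case against.** Keeping expected endpoint events off the AE page is a stated and defensible design choice. The data are not lost either: symptoms, severity, duration, diagnosis and outcome are all on the ILI CRF. The exploratory objectives and analyses are redacted, so a summary of ILIs by arm may already be planned. All of this stands, and the point is therefore confined to the AE and SAE proportions in the visible text.

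A reader might infer that these illnesses never reach the AE table. The documents do not support that. Sections 8.2.1 and 8.10.6.1 and Appendix 2 leave a route open, and the ILI-visit instructions place the exclusion directly after the instruction to record AEs. What remains is that 8.2.1, 8.4.1 and 8.10.6.1 all refer to 8.4.7, so a careful site lands on the broader rule.

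The note may be meant only for serious events. It follows a paragraph on events that may meet the SAE definition. That reading is fair, but it does not settle the matter: a related, nonserious ILI would then have no stated route at all. The note needs correcting either way.

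A reader might also infer that the more reactogenic arm loses more events, since in Days 1 to 7 the investigator separates ILI from reactogenicity. The default in 8.10.6 is that overlapping symptoms do not trigger an ILI visit. The e-diary captures them in the reactogenicity subset, and 8.3.4 has them reported as AEs outside it. Participants and evaluating staff are blinded. An imbalance is possible, but nothing in the documents shows one.

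**Conclusion.** The point holds as a contradiction within the protocol, with a known direction where 8.4.7 is followed: the 4-week AE rate is too low and, on a literal reading of the note, the SAE rate is too high. The AE effect is confined to ILIs with onset through Visit 3. Its size cannot be derived, because the documents give no ILI, AE or relatedness rates. The 0.8 to 4.75 points (0.72 to 4.70 after allowing for ILIs filed as SAEs) and the 2 to 90 extra SAEs per 18,100 rest wholly on the assumed inputs and on full adherence to 8.4.7.

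Two further inferences go too far. One is that every ILI in Days 1 to 14 is lost. The Day 15 limit is in the SAP endpoint and the protocol's estimand and analysis text, but not in the Table 1 definitions. Whether an early ILI counts as potentially consistent with an endpoint is therefore unsettled. The other is that most respiratory illness is missing. A per-protocol ILI needs a respiratory and a systemic symptom together, and both symptom lists are redacted, so that share cannot be judged.

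**What to change.** 1. In Protocol 8.4.7, change the note so that such events are recorded as an AE or an SAE according to Section 10.2. Reconcile 8.2.1, 8.4.1, 8.4.7, 8.10.6.1, 10.2.1 and 10.2.3, including the *any* versus *primary* endpoint wording in 8.4.7, and state how nonserious non-endpoint ILIs are handled.
2. In SAP 3.1.2.4 and 6.1.3, derive from the ILI CRF the nonserious ILIs with onset through Visit 3 that central testing finds influenza-negative. Present any AE through 4 weeks with and without them, by arm and age stratum.
3. List influenza-confirmed ILIs with onset before Day 15 in a separate row by arm. They should not be counted as AEs, because Section 10.2.1 excludes the disease under study.

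The cost is a wording change, one derivation from data already collected, and a few table rows. The AE rate will be somewhat higher in the version that includes these episodes. Working from the ILI CRF also avoids asking sites to re-enter events retrospectively: by Amendment 4, about 19,000 participants had already received qIRV across this study and the Phase 1/2 study.
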